2.4 STUDY DESIGN AND DURATION

2.4.1 Summary of Study Design

This is an open-label, Phase I study in patients with locally advanced or metastatic MEL, NSCLC, or carcinoma. The study has 5 parts.

Part A (including Part A-1 and A-2)

Part A dose escalation will use a 3+3 design and will enroll cohorts of 3-6 patients with MEL or any type of carcinoma sequentially at escalating doses of 1, 3 and 10 mg/kg. Dose escalation will continue until identification of a MTD, up to a maximum dose of 10 mg/kg. Following completion of the dose escalation, additional patients will be enrolled in Part A-1 and Part A-2 as described in Section 1.6 to further define the PK and pharmacodynamic characteristics.

Radiological assessment of tumor response status should be performed approximately every 2 months for the first 12 months of treatment and approximately every 3 months thereafter. (If considered more appropriate by the investigator, disease monitoring by radiological imaging can continue at 2-month intervals beyond the first 12 months). The same imaging technique as used at baseline has to be used throughout the study.

Patients will be monitored for safety, anti-pembrolizumab (MK-3475) antibodies and efficacy throughout the study. If available and consented by participating patients, archived tumor tissue will be collected. In Part A, newly obtained tumor biopsies may be performed for biomarker analysis in select patients with readily accessible tumor lesions and who consent to the biopsies. Ideally, follow-up biopsy should be taken from the same tumor lesion as the baseline biopsy.

In patients who discontinue study therapy early without documented disease progression, every effort should be made to continue monitoring their disease status by radiologic imaging following the guidelines described in Section 3.2.5.4.8 (Duration of Follow-up).

The primary data used for dose escalation and confirmation will be dose limiting toxicity (DLT) in Cycle 1.

With Amendment 10 tumor imaging will be performed approximately every 16 weeks (112 days) (± 28 days) from the first dose of study medication through Year 3, and then Q6 months (24 weeks) (± 28 days) through Years 4 and 5. After 5 years, imaging will be performed annually or per institutional standard of care. Response status will be assessed by the study site. Refer to Section 3.3.1.3 of the protocol for additional information. The same imaging technique must be used in a patient throughout the study. After first documentation of response or progression, repeat imaging will be required approximately 4 weeks later for confirmation, as per immune related response criteria (irRC) guidelines (see Appendix 6.5), (see Section 2.4.1).

Part B

Part B will only enroll patients with MEL. Pembrolizumab (MK-3475) will be administered at 2 mg/kg and 10 mg/kg. The dosing interval to be used in Part B for patients who consent under protocol Amendment 02 will be repeated Q2W. These patients will continue Q2W dosing until they discontinue study therapy. For patients consented under Amendments 03, 04, 05, 06, or following approval of the administrative

memo dated 06-Jan-2012, dosing will be Q3W. Patients consented under protocol Amendment 07 will be administered 10 mg/kg at either Q2W or Q3W.

It is expected that Part B will enroll approximately 506 patients, including 76 ipilimumab-naïve patients: approximately 61 patients at 10 mg/kg; and 15 patients at 2 mg/kg. Part B will also include approximately 40 patients who had previously received ipilimumab (at 10 mg/kg), approximately 80 patients who are ipilimumab refractory at 2 mg/kg Q3W and 80 patients who are ipilimumab refractory at 10 mg/kg Q3W. Amendment 07 will enroll approximately 115 additional patients at 10 mg/kg Q2W and another 115 patients at 10 mg/kg Q3W irrespective of their prior ipilimumab status (i.e., ipilimumab naïve or previously treated). The first 13 patients enrolled in Part B will be required to be ipilimumab-naïve.

Tumor Assessment in Part B

In general, response criteria and patient management will follow the recently described principles and guidelines for immunotherapies of solid tumors [18]. These irRC take into account the observation that some patients with MEL can have a transient tumor flare/tumor progression in the first few months after start of immunotherapy with subsequent disease response. All clinical decisions will be based on the interpretation of the investigator at the site treating the patient in real time.

After radiological tumor assessment at screening, the first radiological assessment of tumor response status will be performed at Week 12 (\pm 1 week), unless there is clinical indication warranting earlier radiologic imaging. The same imaging technique as used at baseline has to be used throughout the study.

If imaging at 12 weeks shows stable disease (SD), treatment will be continued and the next imaging studies will be conducted approximately at Week 24.

If imaging at 12 weeks shows a complete response (CR) or partial response (PR), tumor imaging will be repeated at approximately Week 16 to confirm response, per irRC recommendations. Patients will then return to regular scheduled imaging at approximately Week 24, and every 12 weeks subsequently.

If imaging at 12 weeks shows PD, it is at the discretion of the investigator to keep a patient on study treatment or to stop study treatment until repeat imaging will be repeated approximately 4 to 6 weeks later, in order to confirm PD. Patients that are deemed clinically unstable are not required to have repeat imaging for confirmation. This decision will be based on clinical judgment of a patient's overall clinical condition, including performance status, clinical symptoms, and laboratory data. The patient must meet the following minimal criteria to continue on study between the first radiological indication of progression and confirmation of progression:

1. Absence of symptoms and signs indicating clinically significant PD (including worsening of laboratory values) indicating disease progression.

2. No decline in ECOG performance status
3. Absence of rapid progression of disease or of progressive tumor at critical anatomical sites (e.g., cord compression) requiring urgent alternative medical intervention.

If repeat imaging shows an objective response or stable disease, treatment with pembrolizumab (MK-3475) will continue/ resume and the next imaging studies will be conducted approximately at Week 24, and every 12 weeks subsequently. If repeat imaging at Week 16 confirms PD, patients will be discontinued from study therapy. Note: If repeat imaging shows a reduction in the tumor burden compared to the Week 12 scan demonstrating PD, then treatment with pembrolizumab (MK-3475) may continue after Sponsor approval.

The same paradigm for confirmatory scans of response (4 weeks after the initial finding) or progression of disease (4 to 6 weeks after the initial finding) is applicable to subsequent planned scanning intervals (e.g., Week 24, Week 36, etc.).

Patients will be monitored regularly for safety, efficacy and anti-pembrolizumab (MK-3475) antibodies throughout the study, as per the guidelines in Section 1.7. Newly obtained tumor biopsies for biomarker analysis are mandatory prior to the first dose at baseline. If accessible, archived tumor tissue should be also collected for biomarker analysis. Additional tumor biopsies while on study therapy or after discontinuation of study therapy are highly desirable, for comparison of biomarkers to baseline. Timing of the additional biopsies should follow the guidelines described in Section 1.7. If feasible, follow-up tumor biopsies should be ideally taken from the same lesion as the baseline biopsy. All tumor biopsies require prior written patient consent.

In patients who discontinue study therapy early without documented disease progression, every effort should be made to continue monitoring their disease status by radiologic imaging following the guidelines described in Section 3.2.5.4.8 (Duration of Follow-up).

With Amendment 10 tumor imaging will be performed approximately every 16 weeks (112 days) (± 28 days) from the first dose of study medication through Year 3, and then Q6 months (24 weeks) (± 28 days) through Years 4 and 5. After 5 years, imaging will be performed annually or per institutional standard of care. Response status will be assessed by the study site. Refer to Section 3.3.1.3 of the protocol for additional information. The same imaging technique must be used in a patient throughout the study. After first documentation of response or progression, repeat imaging will be required approximately 4 weeks later for confirmation, as per immune related response criteria (irRC) guidelines (see Appendix 6.5), (see Section 2.4.1).

Part C

Part C will only enroll patients with NSCLC who have experienced progression after two prior systemic anti-tumor regimens. Pembrolizumab (MK-3475) will be administered at a preliminary RP2D, 10 mg/kg. Dosing in Part C will be repeated every 3 weeks. Study

treatment will continue until disease progression, unacceptable toxicity, or the investigator considers it in the best interest of a patient to discontinue study therapy.

Patients will be monitored regularly for safety, efficacy and anti-pembrolizumab (MK-3475) antibodies throughout the study, as per the guidelines in Section 1.7. Newly obtained tumor biopsies for biomarker analysis are mandatory prior to the first dose at baseline. If accessible, archived tumor tissue should be also collected for biomarker analysis. Tumor biopsies require prior written patient consent.

It is expected that Part C will enroll approximately 35 patients at 10 mg/kg.

Tumor Assessment in Part C

With the exception of imaging timelines (described below), the response criteria and patient management will follow the described principles and guidelines as per Part B.

For patients in Part C, following radiological tumor assessment at screening, the first radiological assessment of tumor response status will be performed at Week 9 (\pm 1 week), unless there is clinical indication warranting earlier radiologic imaging. The same imaging technique as used at baseline has to be used throughout the study.

If imaging at 9 weeks shows stable disease (SD), treatment will be continued and the next imaging studies will be conducted approximately at Week 18.

If imaging at 9 weeks shows a complete response (CR) or partial response (PR), tumor imaging will be repeated at approximately Week 13 to confirm response, per irRC recommendations. Alternatively, patients may wait until the beginning of Week 18 for repeat imaging. Following Week 18, tumor imaging will be conducted approximately every 9 weeks subsequently.

If imaging at 9 weeks shows PD, it is at the discretion of the investigator to keep a patient on study treatment or to stop study treatment until repeat imaging will be repeated approximately 4 to 6 weeks later, in order to confirm PD. Patients that are deemed clinically unstable are not required to have repeat imaging for confirmation. This decision will be based on clinical judgment of a patient's overall clinical condition, including performance status, clinical symptoms, and laboratory data. The patient must meet the following minimal criteria to continue on study between the first radiological indication of progression and confirmation of progression:

1. Absence of symptoms and signs indicating clinically significant PD (including worsening of laboratory values) indicating disease progression.
2. No decline in ECOG performance status
3. Absence of rapid progression of disease or of progressive tumor at critical anatomical sites (e.g., cord compression) requiring urgent alternative medical intervention.

If repeat imaging shows an objective response or stable disease relative to baseline, treatment with pembrolizumab (MK-3475) will continue/ resume and the next imaging studies will be conducted approximately at Week 18, and every 9 weeks subsequently. If repeat imaging at Week 13 confirms PD, patients will be discontinued from study therapy. Note: If repeat imaging shows a reduction in the tumor burden compared to the Week 9 scan demonstrating PD, then treatment with pembrolizumab (MK-3475) may continue after Sponsor approval.

The same paradigm for confirmatory scans of response (4 weeks after the initial findings) or progression of disease (4 to 6 weeks after the initial finding) is applicable to subsequent planned scanning intervals (e.g., Week 18, Week 27, etc.).

Tumor imaging will be performed approximately every 9 weeks (63 days) (± 28 days) from the first dose of study medication through Year 2, then Q16 weeks (112 days) (± 28 days) through Year 3, and Q6 months (24 weeks) (± 28 days) through Years 4 and 5. After 5 years, imaging will be performed annually or per institutional standard of care. Response status will be assessed by the study site. Refer to Section 3.3.1.3 of the protocol for additional information. If a tumor biopsy was obtained from a target lesion during eligibility assessment, it is preferred to obtain a new baseline scan. The same imaging technique must be used in a patient throughout the study. After first documentation of response or progression, repeat imaging will be required approximately 4 weeks later for confirmation, as per immune related response criteria (irRC) guidelines (see Appendix 6.5), (see Section 2.4.1).

Part D

Part D will only enroll patients with MEL. Pembrolizumab (MK-3475) will be administered at 2 mg/kg and 10 mg/kg. The dosing interval used in Part D will be Q3W. Study treatment will continue until disease progression, unacceptable toxicity, or the investigator considers it in the best interest of a patient to discontinue study therapy.

It is expected that Part D will enroll approximately 88 ipilimumab-naïve patients: approximately 44 patients at 2 mg/kg and 44 patients at 10 mg/kg. Patients will be randomized 1:1 and assigned to a treatment group manually by the Sponsor based on a computer-generated allocation schedule.

Tumor Assessment in Part D

The response criteria and patient management will follow the described principles and guidelines as per Part B.

With Amendment 10 tumor imaging will be performed approximately every 16 weeks (112 days) (± 28 days) from the first dose of study medication through Year 3, and then Q6 months (24 weeks) (+/- 28 days) through Years 4 and 5. After 5 years, imaging will be performed annually or per institutional standard of care. Response status will be assessed by the study site. Refer to Section 3.3.1.3 of the protocol for additional information. The same imaging technique must be used in a patient throughout the study.

After first documentation of response or progression, repeat imaging will be required approximately 4 weeks later for confirmation, as per immune related response criteria (irRC) guidelines (see Appendix 6.5), (see Section 2.4.1). Refer to Part A, B, D flowchart in Section 1.7.

Part F

Part F will enroll approximately 480 patients with NSCLC. All patients in F-1 and most patients in F-2 must have tumors that express PD-L1 to be eligible for enrollment. In F-1, 88 patients whose tumors express PD-L1 and are naïve to systemic treatment will be randomized 1:1, manually by the Sponsor based on a computer-generated allocation schedule, to 10 mg/kg Q2W (44 patients) and 10 mg/kg Q3W (44 patients) using an allocation schedule generated in-house. Under Amendment 06, 32 patients whose tumors express PD-L1 and have had at least two prior lines of systemic therapy will be treated with pembrolizumab (MK-3475) at 10 mg/kg Q3W. Under Amendment 07 and beyond, in F-2, an additional 280 patients with 1 or more prior systemic treatments will be treated, 168 at 10 mg/kg Q3W and 112 at 10 mg/kg Q2W. Patients will be randomized 3:2 and assigned to a treatment group manually by the Sponsor based on a computer-generated allocation schedule. These patients in F-2 may be stratified by either weak or strong PD-L1 expression level. Enrollment of patients with weakly positive tumor expression of PD-L1 will be limited to approximately 50% of the Q2W and Q3W patient cohorts. Furthermore, in F-2, forty patients whose tumors do not express PD-L1 and have received at least two prior lines of systemic therapy will receive 10 mg/kg Q2W. Under Amendment 09, an additional 40 patients with one or more prior systemic treatments whose tumors express PD-L1 will be enrolled at 2 mg/kg Q3W. Once a patient is eligible for treatment, the Sponsor will inform the site of the appropriate dose to administer.

Tumor Assessment in Part F:

The response criteria and patient management will follow the described principles and guidelines as per Part C.

Tumor imaging will be performed approximately every 9 weeks (63 days) (± 28 days) from the first dose of study medication through Year 2, then Q16 weeks (112 days) (± 28 days) through Year 3, and Q6 months (24 weeks) (± 28 days) through Years 4 and 5. After 5 years, imaging will be performed annually or per institutional standard of care. Response status will be assessed by the study site. Refer to Section 3.3.1.3 of the protocol for additional information. If a tumor biopsy was obtained from a target lesion during eligibility assessment, it is preferred to obtain a new baseline scan. The same imaging technique must be used in a patient throughout the study. After first documentation of response or progression, repeat imaging will be required approximately 4 weeks later for confirmation, as per immune related response criteria (irRC) guidelines (see Appendix 6.5), (see Section 2.4.1). Refer to Parts C and F flowchart in Section 1.7.

2.4.2 Definition of Dose-Limiting Toxicities

All toxicities will be graded using National Cancer Institute (NCI) CTCAE Version 4.0 (Appendix 6.4).

The occurrence of any of the following toxicities during Cycle 1 will be considered a DLT, if judged by the investigator to be possibly, probably or definitely related to study drug administration:

1. Grade 4 non-hematologic toxicity (not laboratory).
2. Grade 4 hematologic toxicity lasting ≥ 14 days.
3. Grade 3 non-hematologic toxicity (not laboratory) lasting >3 days despite optimal supportive care.
4. Any Grade 3 non-hematologic laboratory value if:
 - Medical intervention is required to treat the patient, or
 - The abnormality leads to hospitalization, or
 - The abnormality persists for >1 week.
5. Febrile neutropenia Grade 3 or Grade 4:
 - Grade 3 is defined as ANC $<1000/\text{mm}^3$ with a single temperature of $>38.3^\circ\text{C}$ (101°F) or a sustained temperature of $\geq 38^\circ\text{C}$ (100.4 degrees F) for more than one hour
 - Grade 4 is defined as ANC $<1000/\text{mm}^3$ with a single temperature of $>38.3^\circ\text{C}$ (101°F) or a sustained temperature of $\geq 38^\circ\text{C}$ (100.4°F) for more than one hour, with life-threatening consequences and urgent intervention indicated.
6. Thrombocytopenia $<25,000/\text{mm}^3$ if associated with:
 - A bleeding event which does not result in hemodynamic instability but requires an elective platelet transfusion, or
 - A life-threatening bleeding event which results in urgent intervention and admission to an Intensive Care Unit
7. Grade 5 toxicity (i.e., death).

Replacement of Patients in DLT Period

Patients who received $<90\%$ of the pembrolizumab (MK-3475) infusion in Cycle 1 (e.g., because the infusion had to be discontinued due to an infusion reaction) and did not experience a DLT will not be taken into account in the assessment of the overall DLT rate for the particular dose level cohort and need to be replaced.

If a patient experiences a DLT in Cycle 1, study therapy may be discontinued following discussion and agreement between the Sponsor and investigator. An alternative consideration may be dose modification of pembrolizumab (MK-3475) as described in Section 3.2.5.4.4 with continued therapy.

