
Grades 3 or 4 Grade 3: Prolonged (ie, not rapidly responsive to symptomatic medication and/or brief interruption of infusion); recurrence of symptoms following initial improvement; hospitalization indicated for other clinical sequelae (eg, renal impairment, pulmonary infiltrates) Grade 4: Life-threatening; pressor or ventilatory support indicated
	
Stop Infusion. Additional appropriate medical therapy may include but is not limited to: Epinephrine** IV fluids Antihistamines NSAIDs Acetaminophen Narcotics Oxygen Pressors Corticosteroids Increase monitoring of vital signs as medically indicated until the participant is deemed medically stable in the opinion of the investigator. Hospitalization may be indicated.
	
No subsequent dosing

**In cases of anaphylaxis, epinephrine should be used immediately. Participant is permanently discontinued from further study drug treatment.
 
Note: Appropriate resuscitation equipment should be available at the bedside and a physician readily available during the period of drug administration. For further information, please refer to the Common Terminology Criteria for Adverse Events v4.0 (CTCAE) at http://ctep.cancer.gov
		

Other Allowed Dose Interruption for Pembrolizumab

Pembrolizumab may be interrupted for situations other than treatment-related AEs such as medical / surgical events or logistical reasons not related to study therapy. Participants should be placed back on study therapy within 3 weeks of the scheduled interruption, unless otherwise discussed with the Sponsor. The reason for interruption should be documented in the patient's study record.

3.2.5.4.4.1 Adverse Events of Special Interest: Immune Related Adverse Events

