3.5.4.2 Safety Analysis

The All Patients as Treated (APaT) population will be used for the analysis of safety data in this study. The APaT population consists of all patients who received at least 1 dose of study treatment.

In order for a patient to be considered evaluable for the analysis of DLT, the patient must have either had a DLT in Cycle 1 or had received at least 90% of the prescribed dose of pembrolizumab (MK-3475) in Cycle 1 and completed all safety evaluations up to and including at least 28 days after the first administration of pembrolizumab (MK-3475) without experiencing a DLT. A patient without a DLT will be replaced if he/she did not adequately complete the evaluation period associated with the first cycle of study therapy (i.e., discontinued prematurely due to a reason unrelated to study therapy) or if that patient received <90% of the prescribed dose.

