3.5.5.5 Safety Analysis

Safety and tolerability will be assessed by clinical review of all relevant parameters including DLTs, other AEs, laboratory tests, ECG measurements, and vital signs.

DLTs will be listed. At the end of the trial, a dose-response relationship for the rate of experiencing a DLT in Cycle 1 will be estimated using the pooling-of-adjacent-violators algorithm. This dose-safety estimation will be used to support determination of the MTD. The dose-response relationship, overall tolerability and safety profile, and the PK and PD data will inform the determination of a recommended Phase 2 dose.

Note: As of Amendment 11, PK analyses will not be performed (see Section 3.3.2).

The 80% confidence intervals and Bayes credible intervals for DLT and drug-related toxicity rates in Cycle 1 for an identified MTD level will be provided. Summary statistics (median and range) for time to onset of first drug-related toxicity in each dose level will be provided. Adverse experiences will be summarized as counts and frequencies for each dose level. Laboratory assessments, vital signs, and other safety endpoints will be summarized as appropriate.

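### The DLT definition omits Grade 4 non-hematologic laboratory values while Grade 3 values can count, so the Cycle 1 DLT rate can be understated

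*Combined protocol and SAP*

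**What the plan says.** Section 2.4.2 lists seven kinds of Cycle 1 event that count as a DLT when the investigator considers them at least possibly drug-related. Three matter here:

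- Item 1 is "Grade 4 non-hematologic toxicity (not laboratory"), with no further condition.
- Item 4 begins "Any Grade 3 non-hematologic laboratory value if" and then requires medical intervention, hospitalization or persistence beyond one week.
- Item 2 is "Grade 4 hematologic toxicity lasting ≥ 14 days".

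The same section deals with patients given less than 90% of the Cycle 1 infusion. Such a patient, for example "because the infusion had to be discontinued due to an infusion reaction) and did not experience a DLT will not be taken into account" for the DLT rate and is replaced. Section 3.5.4.2 repeats the 90% rule. It also replaces patients who do not complete the evaluation period, glossed as "discontinued prematurely due to a reason unrelated to study therapy".

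These counts have two uses. Section 2.4.1 makes Cycle 1 DLTs the primary data for escalation. Section 3.5.5.5 says that "a dose-response relationship for the rate of experiencing a DLT in Cycle 1 will be estimated" by pooling adjacent violators, in support of the MTD, with 80% intervals at an identified MTD.

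**The concern.** Severity should not move an event out of the definition. As written, a drug-related Grade 3 transaminase rise that needs treatment is a DLT, and a Grade 4 rise appears in no item. Nothing in the text says that item 4 was meant to include Grade 4.

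A site or analyst who applies the list literally would record no DLT for the more severe event. The cohort could then escalate where it would otherwise have expanded or stopped, and the end-of-trial dose-response estimate and its intervals would inherit the undercount. With about three patients per level, one event matters: it is the difference between 0/3 and 1/3.

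**Working it through.** **Step 1. Coverage of the list in Section 2.4.2.**

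| Type of event | Grade 3 | Grade 4 |
|---|---|---|
| Non-hematologic, not laboratory | Item 3, if longer than 3 days despite supportive care | Item 1 |
| Non-hematologic laboratory | Item 4, under any of three conditions | None |
| Hematologic | Item 5 (febrile neutropenia) | Item 2 if at least 14 days; item 5 (febrile neutropenia) |

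Item 6 concerns low platelets with bleeding, and item 7 is death. One cell is empty.

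**Step 2. Direction and size.** The documents give no operating characteristics for the DLT endpoint, so there is no planned figure to reproduce. They name a 3+3 design without its numerical rule. I assume the usual one: escalate on 0/3, or on 1/6 after expansion. With per-patient counted DLT probability p:

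P(escalate) = (1−p)³ + 3p(1−p)² × (1−p)³

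At p = 0.30 this is 0.343 + 0.441 × 0.343 = 0.494. If a share m of events falls in the empty cell, the counted rate is p(1−m). The values of m are assumptions.

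| m | Counted rate | P(escalate) |
|---|---|---|
| 0 | 30% | 49% |
| 5% | 28.5% | 53% |
| 10% | 27% | 56% |
| 20% | 24% | 62% |
| 30% | 21% | 69% |

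The bounding case is a dose whose only drug-related events are uncounted Grade 4 laboratory values. Escalation is then certain. If the events counted, it would have probability 91%, 71% or 49% at true rates of 10%, 20% or 30%.

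**Step 3. Data reported so far.** Section 3.1.2 gives nine patients completing the 28-day period, three per dose, with no DLT and no drug-related event of Grade 3 to 5. There is nothing to reclassify. The exact 80% interval has an upper limit of 54% for 0/3 and 23% for 0/9 pooled.

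**Step 4. The exclusion rule.** Suppose 20% of fully infused patients have a DLT, and 10% of all patients are stopped below 90% of the infusion without one (both assumed).

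- Excluded: 20%, P(escalate) 71%.
- Kept as non-events: 0.9 × 20% = 18%, P(escalate) 75%.
- Counted as events: 18% + 10% = 28%, P(escalate) 54%.

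Exclusion gives a lower rate than counting these stops as events, and a higher one than keeping them as non-events.

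**Step 5. Whether exclusions are visible.** Section 1.5 and Table 2-1 give 10 escalation patients against nine completers. Table 3-1 notes one discontinuation at 1 mg/kg without a reason. If this is the missing patient, which is an inference, that dose moves from 0/3 (80% interval 0 to 54%) to 0/4 (0 to 44%) as a non-event or 1/4 (3 to 68%) as an event.

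**The case against.** The strongest reply is that the gap is narrow and has had no visible effect. Hematologic Grade 4 events are covered, conditionally, by item 2. Section 3.4.6 records each change of grade within an episode, so a value that passes through Grade 3 may still meet item 4. Section 3.5.5.5 already plans Cycle 1 drug-related toxicity rates and adverse event summaries by dose level, and the recommended Phase 2 dose also rests on overall safety, PK and pharmacodynamics. Enrollment is complete, and Section 3.1.3 justifies the current fixed dose on other evidence. All of this limits the consequence. It does not fill the empty cell: the planned drug-related toxicity intervals apply only at an identified MTD, and they do not feed the dose-response estimate, which is still to be made at the end of the trial.

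A reader might also infer that the 90% rule by itself biases the DLT rate low, because an infusion reaction is drug-caused and Table 3-3 gives "No subsequent dosing" after a Grade 3 or 4 reaction. The documents do not support that. The rule is the same in Sections 2.4.2, 2.7.2 and 3.5.4.2, and it removes only patients without a DLT. A reaction that meets item 1 or item 3 still counts. The rate is low only if the remaining stops ought to be DLTs, which is a clinical decision. Nor do the stopping rules in Tables 3-2 and 3-3 contradict the DLT list: Section 2.4.2 lets a patient with a DLT continue treatment, so the two are separate questions.

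A further inference would be that a fully infused patient who stops for a drug-related reason cannot be evaluable. Cycle 1 in dose escalation is one infusion and 28 days. Evaluability requires safety evaluations to day 28, not continued treatment. Section 3.2.5.7 separates stopping treatment from leaving the study, and Section 3.2.5.4.7 follows patients for at least 30 days after the last dose unless new anticancer therapy begins. Such a patient can still be evaluable.

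**Conclusion.** The point holds for Grade 4 non-hematologic laboratory values. Items 1 and 4 of Section 2.4.2 leave them outside every DLT criterion while the milder grade can count. Followed literally, this can understate the Cycle 1 DLT rate used for escalation and for the estimate and intervals in Section 3.5.5.5.

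The size depends on assumptions that the documents do not supply: the escalation rule, the true rate, and the share of events in the gap. The 49% to 56–69% shift is illustrative, and certain escalation is a bound. It would be wrong to conclude that the reported Part A rate is biased, since the preliminary data contain no event that the gap could have hidden.

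The exclusion rule raises only a reporting need. Its effect depends on how excluded patients are regarded, so the reader should be able to see who they are and why they were excluded.

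**What to change.** 1. In Section 2.4.2, reconcile items 1 and 4 so that a Grade 4 non-hematologic laboratory value is classified consistently with a Grade 3 value. The sponsor sets the clinical rule.
2. In Section 3.5.5.5, list by dose level, with reasons, the treated Part A patients excluded from the DLT rate, including those whose infusion was stopped below 90% for an infusion reaction.
3. Beside the protocol-defined rate, report by dose level one sensitivity Cycle 1 rate among all treated Part A patients. It should add drug-related Grade 4 laboratory values and drug-related permanent discontinuations to the protocol-defined events. It is a sensitivity figure and does not redefine a DLT.

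The cost is a wording change and one extra tabulation from safety data that the protocol already has sites record. The sensitivity rate may look slightly less favourable than the protocol-defined one.
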